8 PATIENT POPULATION

A maximum of 200 patients at 45 centers worldwide will be enrolled. Thirty feasibility patients will be enrolled at approximately 7 - 10 centers and 170 pivotal patients will be enrolled at approximately 45 centers worldwide. A minimum of 114 pivotal patients will be enrolled at US centers.

The 12-month data from at least 156 evaluable pivotal patients, as well as detailed summary data on the 30 feasibility patients will be submitted to FDA to support a Pre-Market Approval (PMA) application.

Patients will include symptomatic adults ≥18 years of age with clinically significant chronic non-malignant obstruction of the iliofemoral venous outflow tract.

8.1 Initial DSMB Safety Evaluation

Thirty (30) patients will be enrolled at approximately 7 centers. These patients will not be included in the pivotal study population, but will be evaluated separately for the primary safety and efficacy endpoints as well as for all secondary endpoints. When these 30 patients have completed their 30-day follow-up, a Data Safety Monitoring Board (DSMB) will review the safety data and will determine if the study can proceed with enrollment of the pivotal population. The DSMB report will be submitted to FDA for reference.

STE-HUM-007P US Clinical Protocol Revision C

8.2 Inclusion/Exclusion Criteria

Patients meeting all pre-procedural inclusion and exclusion criteria will have the study presented to them. Patients giving informed consent will complete protocol-required testing, undergo baseline evaluation, and undergo the protocol-defined determination of binary stenosis, as measured by venogram. Patients meeting the venogram binary stenosis definition, as determined by the treating physician, will undergo the protocol-defined stenting procedure and all protocol-defined follow-up visits.

- 8.2.1 Inclusion Criteria Pre-Procedural Criteria
 - 1. Age ≥18 years
 - 2. Willing and capable of complying with all follow-up evaluations at the specified times
 - 3. Able and willing to provide written informed consent prior to study specific procedures
 - Presence of unilateral, clinically significant, chronic non-malignant obstruction of the common femoral vein, external iliac vein, common iliac vein, or any combination thereof, defined as a ≥50% reduction in target vessel lumen diameter (to be measured by venogram during procedure, per Exclusion 25).
 - 5. Clinically significant venous obstruction defined as meeting at least one of the following clinical indicators:
 - Clinical severity class of CEAP classification ≥3 (See Appendix 4.)
 - VCSS Pain Score ≥2 (See Appendix 7.)
 - 6. Negative pregnancy test in females of child-bearing potential
 - 7. Intention to stent the target lesion only with the Veniti Vici Venous Stent
- 8.2.2 Exclusion Criteria Pre-Procedural Criteria
 - 8. Presence or history of clinically significant pulmonary emboli within 6 months prior to enrollment.
 - 9. Venous obstruction that extends into the inferior vena cava
 - 10. Contralateral disease of the common femoral vein, external iliac vein, common iliac vein, or any combination thereof with planned treatment within 30 days after subject enrollment
 - 11. Life expectancy <12 months
 - 12. Female of childbearing potential who is pregnant or plans to become pregnant during the duration of the clinical study
 - 13. A. Uncontrolled or active coagulopathy ORB. Known, uncorrectable bleeding diathesis with the following definitions:
 - Uncorrected INR ≥2.0 or aPTT ≥1.5 X normal local lab value
 - Platelet count <80,000
 - 14. Uncorrected hemoglobin of ≤9 g/dL

STE-HUM-007P US Clinical Protocol Revision C

- 15. Patients with an estimated glomerular filtration rate (eGFR) <30 mL/min. In patients with diabetes mellitus, eGFR <45 mL/min.
- 16. Known hypersensitivity to nickel or titanium
- 17. Contrast agent allergy that cannot be managed adequately with pre-medication
- Intended concurrent thrombolysis or thrombectomy procedure OR intended or planned (within 30 days) adjuvant procedure such as creation of temporary AV fistula, placement of IVC filter, endovenectomy or saphenous vein ablation
- 19. Current or recent (within 30 days) active participation in another drug or device clinical trial (Participation in observational studies is acceptable.)
- 20. Patient judged to be a poor candidate by the primary investigator
- 21. Patients who have had any prior surgical or endovascular intervention of the target vessel Note: Patients who have had catheter-directed or mechanical thrombolysis in the target vessel for DVT at least 3 month (90 days) prior to the VIRTUS index procedure may be included in the trial.
- 8.2.3 Exclusion Criteria Intra-procedural Criteria
 - 22. Patients in whom the lesions cannot be traversed with a guide wire. These patients will not count against the study sample size.
 - 23. Patients where the obstruction extends into the inferior vena cava or below the level of the lesser trochanter. These patients will not count against the study sample size.
 - 24. Patients whose vein diameters are not within limits stated in current Instructions for Use as determined by venogram. These patients will not count against the study sample size.
 - 25. Patients who do not meet the venogram binary stenosis definition above, as determined by the treating physician. These patients will not count against the study sample size.

9 STUDY PROCEDURES AND DATA COLLECTION

9.1 Patient Screening Procedure

Patients who have been diagnosed with chronic nonmalignant obstruction of the iliofemoral venous segment of either extremity will undergo screening to determine their appropriateness for inclusion in the study.

- Patient medical history and physical examination
- Review of diagnostic investigations to ascertain diagnosis of chronic nonmalignant venous obstruction (See Section 1.)
- The investigator must maintain detailed source documents on all patients who are enrolled or who undergo screening in the study. Investigators will maintain a screening log that must include at a minimum: screening date, enrollment status (enrolled/excluded) and the reason for exclusion for all screen failures.

STE-HUM-007P US Clinical Protocol Revision C

9.2 Informed Consent

All patients who meet the pre-procedural inclusion criteria will have the study presented to them, as well as their family if possible. Patients must document consent to the study by signing the approved consent form. One copy of the informed consent will be placed in the patient's medical record, a second will be given to the patient or representative, and a third may be placed in the study records.

Patients that sign the informed consent will be considered enrolled in the study. These patients should also be entered into the electronic data capture (EDC) system and monitored for protocol deviations and adverse events until discharge from the hospital. Subjects that sign consent, but are found to not meet Inclusion/Exclusion criteria (i.e. screen failures) will not be included in the statistical analysis.

9.3 Baseline Evaluation (within 30 days of implant procedure)

Patients who sign an informed consent will undergo baseline testing:

- History and physical examination
- Laboratory evaluation (CBC and eGFR will be required for all patients; Patients on a Vitamin K antagonist or direct thrombin or Factor Xa inhibitors, prior to the intervention, require a PT with INR; subjects on heparin prior to the intervention require an aPTT. Patients with history of liver disease will require a PT with INR and an aPTT.)
- Medication review
- Pregnancy test in females of child-bearing age (within 48 hours of implant procedure)
- CEAP Assessment (See Appendix 4.)
- CIVIQ-2 Quality of Life questionnaire (See Appendix 5.)
- VAS pain score (See Appendix 6.)
- VCSS (See Appendix 7.)

9.4 **Pre-Procedural Evaluation**

Patients who consent, and who meet the pre-procedural inclusion and exclusion criteria, will undergo baseline venography to verify appropriateness for enrollment, as determined by the treating physician.

- Venography only to ascertain obstruction with at least a ≥50% in the target vessel lumen diameter compared to the normal vein lumen diameter immediately peripheral to the target lesion as measured by venogram. IVUS may not be used to fulfill this requirement.
- Absence of obstruction extending into the inferior vena cava (IVC) as determined by any imaging modality.

9.5 Venous Stent Implant Procedure

9.5.1 Procedure Guidelines

STE-HUM-007P US Clinical Protocol Revision C

Patients who meet all of the inclusion and exclusion criteria will undergo the venous stenting procedure. During the venous stenting procedure, the current Veniti Vici Venous Stent System Instructions for Use will be followed.

- Patients will be monitored, per local institutional guidelines.
- Patients will receive appropriate sedation and anesthesia, per local institutional guidelines.
- Venography will be performed to determine sizing for venous stenting with the Veniti Vici Venous Stent System and to evaluate lesion characteristics.
- IVUS will be performed to confirm sizing for venous stenting with the Veniti Vici Venous Stenting System. Assessment of target lesion presence/absence, lesion severity (maximal binary stenosis), and lesion characteristics, per the case report form (location, length).
- Occluded veins will require guidewire recanalization before stenting.
- The lesion(s) must be adequately covered by the stent(s).
- If 2 or more stents are required to cover the target lesion, the stents will be overlapped by at least 1 cm to insure adequate stent cover without skipped areas.
- The diameter of the stent should be 2 mm greater than ("over") the measured diameter of the surrounding "normal" vessel. The stent should be at least 1 cm longer than the obstructive venous lesion (0.5 cm (peripherally) and 0.5 cm centrally. When selecting stent length, the expected foreshortening should be taken into account.
- 9.5.2 Perioperative Anticoagulation Regimen
 - Patients on long-term warfarin therapy should be bridged prior to the intervention with LMWH or other anticoagulant per local institution guidelines, and will restart warfarin therapy within 24 hours.
 - All patients will receive prophylactic LMWH or other anticoagulant prior to the intervention and following the procedure, per local institutional guidelines.
 - This applies to all patients, including those bridged, as described in Bullet 1 of Section 9.5.2 above.
 - All patients should be appropriately anticoagulated during the procedure, per hospital protocol.
 - SCD compression/early ambulation post-intervention will occur in all patients.

9.5.3 Post-Stent Placement Assessments

• Venography to assess post-procedural target vessel lumen diameter and to determine residual target lesion stenosis. This assessment will serve as the baseline for determining the primary efficacy

STE-HUM-007P US Clinical Protocol Revision C

Confidential

Page 28 of 70

endpoint at the 12 month follow-up (or prior Interval Evaluation, when applicable). When venographic data is available at the 12 month visit, values from the venogram obtained at the Post-Stent Placement will serve as the subject's baseline.

- Adverse event assessment
- Extended Anticoagulation Protocol (See Appendix 2.) Anticoagulation or antiplatelet treatment for concomitant conditions should be continued at the discretion of the enrolling physician. Study patients should also receive anticoagulation or antiplatelet therapy, per the following guidelines. These guidelines apply through the 12 month visit.
 - Patients on extended Vitamin K antagonists or direct thrombin or Factor Xa inhibitors prior to enrollment should continue on warfarin post-procedure with a target INR of 2-3, or within the documented therapeutic range for INR per local guidelines.
 - Patients with a history of ≥2 thrombo-embolic event(s) and not on extended Vitamin K antagonists or direct thrombin or Factor Xa inhibitors prior to enrollment will be anticoagulated following the procedure and continue through the 12 month visit, as per ACCP guidelines⁷ (Vitamin K antagonists such as warfarin to achieve an INR of 2-3 [or an INR within the documented therapeutic range for INR per local guidelines] or direct thrombin or Factor Xa inhibitors such as rivaroxaban per recommended dosing).
 - Patients with a history of <2 prior thrombo-embolic event OR patients with no history, but where the obstruction is determined to be caused by previous silent thrombotic event, will begin anticoagulation post-procedure and continue for 6 months in the case of non-occlusive obstruction (Vitamin K antagonists such as warfarin to achieve an INR of 2-3 [or an INR within the documented therapeutic range for INR per local guidelines], or direct thrombin or Factor Xa inhibitors such as rivaroxaban per recommended dosing). From 6 months through the 12 month visit, these patients should receive low-dose ASA.
 - Patients with occlusive obstruction should receive Vitamin K antagonists such as warfarin to achieve an INR of 2-3 (or an INR within the documented therapeutic range for INR per local guidelines), or direct thrombin or Factor Xa inhibitors such as rivaroxaban per recommended dosing through the 12 month visit.
 - Patients who were on clopidogrel or prasugrel pre-procedure will resume their baseline dose within 24 hours of the procedure and continue as required for the underlying condition UNLESS the enrolling physician believes that the

STE-HUM-007P US Clinical Protocol Revision C

Page 29 of 70

need for anticoagulation outweighs the need for anti-platelet drugs.

- All patients not receiving anticoagulation therapy or antiplatelet therapy as noted above will receive low-dose ASA (i.e. 75 mg, 81mg, etc.) daily throughout the 12 month visit.
- IVUS to assess stent characteristics (apposition, webbing, coverage of target lesion, etc.)
- Physician evaluation of technical difficulty of implantation

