Reference Vein Diameter (RVD)	Reference Vein Diameter (RVD) is defined as the normal diameter of the target vessel (CIV, EIV, or CFV)
Procedural technical success	Achievement of a final residual target vessel diameter stenosis of ≤50% as measured on the post procedural venogram, without skipped lesion regions, with placement of the study device alone with or without post-stenting balloon dilation as needed
POST-PROCEDURAL DEFINITION	DNS
Term	Definition
Device or procedure related death	Death specifically attributable to the Veniti Vici Venous Stent System or the stent placement procedure
Late technical success	 Absence of device movement >10mm related to anatomical landmarks or any migration leading to symptoms or requiring therapy
	 Absence of stent occlusion by thrombosis or restenosis, defined as reduction in treated segment lumen more than 50% from the post-procedure vessel lumen diameter as measured by post-procedural venogram or DUS
	 Structural integrity, defined as the absence of pinching (focal compression), recoil (poor radial resistive force) or kinking (stent bending upon itself) that results in >50% diameter reduction of the stent, or fracture
Patency (Primary Endpoint)	At 12 months post-intervention, freedom from occlusion by thrombosis AND freedom from surgical or endovascular intervention on target vessel with re-stenosis or stent occlusion to maintain patency AND freedom from in stent diameter stenosis more than 50% as measured by venogram. For patients refusing the venographic assessment at 12 months, DUS-determined patency will be used instead

Rate of intervention lesion (RIL)	Re-intervention within the target vessel with in-stent stenosis or thrombosis to achieve patency (constitutes failure on the primary endpoint)
Rate of intervention of extremity (RIE)	Re-intervention of a non-target lesion venous segment of the ipsilateral (target) extremity required to maintain ipsilateral extremity venous outflow (does NOT constitute failure of the primary endpoint)
In-stent stenosis (primary endpoint)	Non-occlusive reduction in the treated segment lumen diameter more than 50% from the post-procedural vessel lumen diameter per venogram or DUS
In-stent thrombosis (primary endpoint)	Occlusion of the stented target vessel due to thrombosis; early thrombosis is that which occurs ≤30 days; late thrombosis is that which occurs >30 days

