	The follow-up period is 60 months.						
Follow-Up	The 12-month data from at least 156 patients will be submitted to FDA to support a Pre-Market Approval (PMA) application.						
Primary Efficacy Endpoint	The primary efficacy endpoint for this study will be the primary patency rate at 12 months post-intervention, defined as freedom from occlusion by thrombosis AND freedom from surgical or endovascular intervention on target vessel which are found to have re-stenosis or stent occlusion to maintain patency AND freedom from in-stent stenosis more than 50% by venogram. For patients refusing the venographic assessment at 12 months, DUS-determined patency will be used instead.						
Primary Safety	The primary safety endpoint for this study will be a composite endpoint of any major adverse event within 30 days, as adjudicated						

Page 14 of 70

Endpoint	by a Clinical Events Committee. Major Adverse Events are listed in Section 11.1.4.							
Secondary Efficacy Endpoint	The formal secondary endpoint for this study will be a binary response variable based on an improvement in VCSS by at least 50% at 12 months post-intervention.							
	 Procedural Endpoints Procedural technical success, defined as achievement of a final residual diameter stenosis of ≤50% as measured by venogram without skipped lesion areas with placement of the study device alone with or without post-stenting balloon dilation 							
Ancillary Analyses	 Lesion success defined as achievement of ≤50% residual diameter stenosis using any percutaneous method (including use of non- study devices) 							
	• Procedural success defined as procedural technical success without the occurrence of major adverse event between the index procedure and discharge							

	Late technical success (through 12 months) defined as:					
	Absence of migration					
	Absence of stent embolization					
Ancillary Analyses (continued)	Achievement of primary patency					
	Structural integrity, defined as the absence of:					
	 Pinching, defined as focal compression of the stent with > 50% diameter reduction of the stent 					
	 Kinking, defined as >50% diameter reduction of the stent with the stent doubling or bending on itself 					
	 Recoil, defined a poor radial resistance to diffuse collapse, which results in >50% diameter reduction of the stent (i.e., stent diameters obtained throughout the study period as compared to the final stent diameter after insertion measured by DUS or venogram). Fracture(s) 					

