9.6 Discharge or Three Days Post-Procedure (whichever comes first)

- Duplex ultrasound to determine post-procedural target vessel lumen diameter (For patients refusing the venographic assessment at 12 months [or prior Interval Evaluation, as applicable], DUS-determined patency will be used instead, with the DUS obtained at the Discharge or Three Days Post-Procedure visit serving as the baseline).
- Determination of discharge
- Anticoagulation Review, based on the Extended Anticoagulation Protocol (See Appendix 2.)
- Adverse event assessment
- Patients who do not meet intra-procedural inclusion criteria (and who do not receive the implanted study device) should be followed only through hospital discharge for protocol deviations and adverse events. This visit will conclude participation for these screen failed patients. These subjects will not be included in the statistical analysis.

9.7 1 Month Evaluation (30 days -7/+14 days)

- Physical examination (to assess for the presence of Adverse Events)
- Anticoagulation Review, based on the Extended Anticoagulation Protocol (See Appendix 2.)

9.8 6 Month Evaluation (180 days ± 30 days)

- Physical examination (to assess for the presence of Adverse Events)
- Duplex ultrasound (required only for first 30 patients to assess patency)
- CIVIQ-2 Quality of Life questionnaire (See Appendix 5.)
- VAS pain score
- VCSS (See Appendix 7.)
- Anticoagulation Review, based on the Extended Anticoagulation Protocol (See Appendix 2.)

9.9 12 Month Evaluation (365 days ± 60 days)

Patients that refuse the venogram and IVUS at this visit should have all other assessments listed here performed:

- Physical examination (to assess for the presence of Adverse Events)
- Assessment of primary patency by venography

STE-HUM-007P US Clinical Protocol Revision C

- Determination of residual external venous segment compression, stent recoil, and lesion coverage by IVUS
- Duplex ultrasound for all patients (For patients refusing the venographic assessment at this visit, DUS-determined patency will be used towards the primary efficacy endpoint instead.)
- Assessment of stent integrity by bi-plane X-Ray (See Appendix 3.)
- CIVIQ-2 Quality of Life questionnaire (See Appendix 5.)
- VAS pain score (See Appendix 6.)
- VCSS (See Appendix 7.)
- Anticoagulation Review, based on the Extended Anticoagulation Protocol (See Appendix 2.)

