15.8 Evaluation of Endpoints

15.8.1 Primary Efficacy Endpoint

The primary efficacy endpoint for this study will be the primary patency rate at 12 months post-intervention. Stented limbs will be assigned the status of *patency failure* if they are known to have a patency failure event:

- Thrombosis including the stented area of the vein
- Re-intervention including the stented area
- Venous imaging study at any time through 12 months showing a restenosis of greater than 50%.

Patients will be assigned the status of *patency success* if their venous imaging study at 12 months showed no greater than 50% restenosis (and no prior study showed greater than 50% restenosis).

STE-HUM-007P US Clinical Protocol Revision C

In the per-protocol (PP) analysis, only patients that meet either of these two criteria will be included. Patients with no imaging study at 12 months and no patency failure event will be ignored in the analysis.

In the worst-case and tipping point analyses, all patients will be included. Patients who were ignored in the PP analysis will be treated as patency failures.

Both the PP and worst-case analyses will test the following hypotheses:

$$\begin{aligned} \mathsf{H}_{0} &: q_{NT} * (p_{NT} - PG_{NT}) + q_{PT} * (p_{PT} - PG_{PT}) \le 0 \\ \mathsf{H}_{A} &: q_{NT} * (p_{NT} - PG_{NT}) + q_{PT} * (p_{PT} - PG_{PT}) > 0, \end{aligned}$$

where p_{NT} and p_{PT} are the observed 12-month patency rates for NT and PT subjects, respectively; PG_{NT} and PG_{PT} are pre-specified fixed performance goals for NT and PT subjects, respectively; and q_{NT} and q_{PT} , both are fixed weights for NT subjects (0.26) and PT subjects (0.74), respectively. The sample weights will not be adjusted based on actual enrollment rates.

The hypothesis test for this endpoint will be tested using a one-sided weighted Z-test at the 0.025 significance level. The test statistic for this hypothesis test is:

$$Z = \frac{q_{NT} * (p_{NT} - PG_{NT}) + q_{PT} * (p_{PT} - PG_{PT})}{\sqrt{q_{NT}^2 * \frac{PG_{NT}(1 - PG_{NT})}{n_{NT}} + q_{PT}^2 * \frac{PG_{PT}(1 - PG_{PT})}{n_{PT}}}$$

where p_{NT} is the proportion of successes in the NT population, PG_{NT} is the performance goal of 85.5% for the NT population, q_{NT} is the predefined weight of 0.266 for the NT population, p_{PT} is the proportion of successes in the PT population, PG_{PT} is the performance goal of 67.9% for the PT population, q_{PT} is the pre-defined weight of 0.74 for the PT population.

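### A vein left more than 50% narrowed after stenting can count as patent at 12 months, because Section 15.8.1 scores only the lumen lost afterwards

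*Combined protocol and SAP*

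**What the plan says.** The plan uses two reference diameters.

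- **Entry and acute result: the normal vein.** Section 1 defines obstruction at entry as a lumen reduction of at least 50% against the normal vein just peripheral to the lesion. Residual stenosis uses the same comparator. Procedural technical success is "Achievement of a final residual target vessel diameter stenosis of ≤50% as measured on the post procedural venogram", with further conditions on skipped regions and use of the study device alone.
- **12-month endpoint: the lumen achieved.** Section 1 defines in-stent stenosis for the primary endpoint as "Non-occlusive reduction in the treated segment lumen diameter more than 50% from the post-procedural vessel lumen diameter per venogram or DUS". Section 9.5.3 says of the post-stent venogram: "This assessment will serve as the baseline for determining the primary efficacy" endpoint. It adds that "values from the venogram obtained at the Post-Stent Placement will serve as the subject's baseline". For patients who refuse the 12-month venogram, Section 9.6 uses duplex ultrasound, "with the DUS obtained at the Discharge or Three Days Post-Procedure visit serving as the baseline".

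The endpoint sentence in the Protocol Summary asks for "freedom from in-stent stenosis more than 50% by venogram" and names no comparator. Section 15.8.1 lists three failure events: thrombosis, re-intervention in the stented area, and "Venous imaging study at any time through 12 months showing a restenosis of greater than 50" per cent. A patient is a success "if their venous imaging study at 12 months showed no greater than 50% restenosis" and no prior study showed more. Residual stenosis is in neither rule. The per-protocol set keeps every patient who meets either rule, so patients with a poor acute result stay in.

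**The concern.** A vein can leave the procedure more than 50% narrowed against the normal vein, which is enough to have entered the trial as obstructed. If it then stays as it is, its loss from baseline is zero and it is scored as patent. The primary endpoint is meant to show that the device achieves patency, and this rule credits it for veins that were not opened to the plan's own threshold.

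A residual above 50% shows up only in the ancillary procedural endpoints, which Section 15.9 reports without hypothesis tests. The trial has one arm and a fixed goal, so no control group is scored by the same rule to offset such patients.

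**Working it through.** **1. The plan's own figure.** Inputs from Section 15.7: goals 0.855 (non-thrombotic, NT) and 0.679 (post-thrombotic, PT); assumed rates 0.955 and 0.779; weights 0.26 and 0.74; one-sided 0.025; 156 evaluable. The plan gives no split of the 156. I take 0.26 × 156 ≈ 41 NT and 115 PT.

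- Null SE = √(0.26²·0.855·0.145/41 + 0.74²·0.679·0.321/115) = 0.0352
- SE at the assumed rates = √(0.26²·0.955·0.045/41 + 0.74²·0.779·0.221/115) = 0.0298
- Power = Φ((0.10 − 1.96·0.0352)/0.0298) = 85.0%

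The plan states 84%. Exact enumeration of the two binomials gives 87.0% for 41/115 and 83.2% for 42/114. The test is therefore understood correctly; the point does not depend on this power figure.

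**2. What the rule lets through.** Stenosis against the normal vein at 12 months = 1 − (1 − residual)(1 − later loss). Success allows a later loss of up to 50%.

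| Residual after stenting | No further loss | Largest 12-month stenosis still scored patent |
|---|---|---|
| 50% | 50% | 1 − 0.5·0.5 = 75% |
| 60% | 60% | 1 − 0.4·0.5 = 80% |
| 70% | 70% | 1 − 0.3·0.5 = 85% |

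The 50% row is a technical success; the other two are technical failures. The last column is the extreme, not the typical case.

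**3. The opposite direction.** Section 9.5.1 sizes the stent 2 mm over the normal vessel, and Section 5.1 gives diameters of 12, 14 and 16 mm. If the stent opens to nominal diameter, half of the post-procedure lumen corresponds to:

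- 12 mm stent, 10 mm vein: 1 − 6/10 = 40.0% stenosis against the normal vein
- 14 mm stent, 12 mm vein: 1 − 7/12 = 41.7%
- 16 mm stent, 14 mm vein: 1 − 8/14 = 42.9%

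In these patients failure begins just beyond 40–43%, earlier than under a 50% normal-vein rule.

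**4. Illustrative size.** Let f be the share of patients scored patent only because residual stenosis is ignored. The documents give no value, so f is an assumption. Suppose patency against the normal vein equals the goal in both strata, and add f to each rate. One point moves Z by 0.01/0.0352 = 0.28; the normal approximation then gives Φ(−1.96 + 0.28) ≈ 4.7%. Exact enumeration for 41/115:

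| f | Z-test alone | Z-test and both observed rates above their goals |
|---|---|---|
| 0 | 2.7% | 2.2% |
| 1% (about 1.6 of 156) | 5.0% | 4.1% |
| 2% (about 3.1) | 8.6% | 7.4% |
| 3% (about 4.7) | about 14% | 12.3% |

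The last column is the closer one to trial success, because Section 15.7 also requires each stratum's observed rate to exceed its goal.

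**The case against.** **The baseline is a deliberate choice, and the acute result is reported.** Measuring durability from the lumen achieved is a legitimate definition of restenosis. Residual stenosis is measured after stenting and enters technical, lesion and procedural success, each reported with a 95% confidence interval. Clinical benefit is tested separately through VCSS. This stands as a reason to keep the baseline. It does not settle how a vein left above 50% should count in the primary endpoint, since those endpoints describe such patients without reclassifying them.

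**A reader might infer that the bias always favours the device.** The documents do not support that. Step 3 shows that a fully opened, oversized stent faces a stricter rule, and the distribution of post-procedure lumens is not given. The direction is certain only for patients left above 50%.

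**A reader might also infer that the type I error is in fact inflated.** That needs goals that mean patency against the normal vein with poor acute results counted as failures. Section 15.5.2 describes the literature rate as freedom from stenosis of 50% or more, without a reference diameter or a rule for technical failures. If the source series also measured loss from the stented lumen, the mismatch with the goal would shrink or vanish.

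**Such patients may be rare.** Lesions that cannot be crossed are excluded, and balloon dilation after stenting is allowed. The technical success above 90% quoted in Section 4.2 is no estimate for this population. Some of these patients would also fail anyway through thrombosis, further loss or re-intervention. Section 9.10 is unclear on the last: one sentence spares a re-intervention when the core laboratory found the vessel patent, and another fails any patient with a further intervention. All of this stands, and it makes f an upper bound on the effect of leaving such veins in.

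**Conclusion.** The gap is real. Sections 1, 9.5.3, 9.6 and 15.8.1 together score a vein with residual stenosis above 50% as a 12-month success unless it loses more than half of its remaining lumen, occludes or has a counted re-intervention. No other section corrects this. Reading the uncommented 50% in the endpoint sentence against the normal vein would contradict the explicit definition in Section 1.

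For these patients the misclassification favours the device. The net effect of the post-procedure baseline over all patients is unknown.

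The size is also unknown. Per assumed point of such patients, the chance of passing at the boundary goes from 2.7% to 5.0% for the Z-test alone, or from 2.2% to 4.1% with the observed-rate conditions. This rests on the 41/115 split and on goals that refer to normal-vein patency. The change is worth making because it is cheap and must be fixed before the data are analysed, not because a large bias has been shown.

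**What to change.** Keep the post-procedure baseline and make two changes.

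1. State in Section 15.8.1 that a patient whose post-stent venogram shows, by core-laboratory reading, residual stenosis above 50% against the normal peripheral vein is a patency failure. Use this criterion alone. The full technical-success definition also covers skipped regions and use of the study device alone, and would fail veins that are open.
2. Add a supportive analysis of 12-month patency with the reference vein diameter as denominator, from the same venograms. State how many patients have only a 12-month duplex study and so cannot enter it. This table also shows the net direction, because it captures the effect of oversized stents.

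The cost is one classification sentence and one table. The venograms are already taken and sent to the core laboratory, so no visit, image or patient is added. The downside is a patency rate that may fall by the few patients concerned.
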